## Schema

## 1.0 Objectives

*This will be a single-center, open-labelled, pilot study. This study has the following objectives:*

### 1.1 Primary Objective

1.1.1 To determine the reduction of thrombin peak concentration and/or endogenous thrombin potential measured by Thrombin Generation Assay (TGA) at 3 months in the “anticoagulation +atorvastatin” arm as compared to the “anticoagulation” arm.

### 1.2 Secondary Objectives

1.2.1 To determine the composite rate of recurrent VTE and VTE related mortality in patients in the statin arm as compared to no statin arm.

1.2.2 To determine the rate of arterial thrombotic events in patients in the statin arm as compared to no statin arm.

1.2.3 To determine the rate of major, non-major, and all hemorrhages defined by the ISTH (International Society on Thrombosis and Haemostasis) criteria (see section 7.3) in patients in the statin arm as compared to no statin arm.

- 1.2.4 To evaluate the changes in proposed hemostatic, inflammatory, and lipidomic biomarkers at 3 and 9 months compared to upon enrollment in patients in both arms.
- 1.2.5 To determine the rate of residual vein obstruction by Doppler ultrasound at 3 months in patients in the statin arm as compared to no statin arm.
- 1.2.6 To determine the rate of clinical post-thrombotic syndrome (PTS), as objectively evaluated with Villalta scoring system in patients in the statin arm as compared to no statin arm.

## 2.0 Background

Venous thromboembolism (VTE) refers to the formation of pathological blood clots in extremity veins (deep vein thrombosis, DVT) and/or pulmonary arteries (pulmonary embolism, PE). VTE is common, with an estimated incidence of 1-2 per 1000 in the general population, and increases to over 1% in the elderly. VTE is a considerable public health threat. Approximately 300,000-600,000 patients develop VTE in the United States each year, accounting for 60,000-100,000 deaths. According to the Healthcare Cost and Utilization Project, about 350,000 hospital admissions were due to VTE, costing over three billion dollars in 2011 alone. In addition, approximately one third of patients die within one year of their initial VTE, and one third of survivors suffer from long-term morbidity.

Anticoagulation is the current standard of care for acute VTE. However, even after a course of anticoagulation, 30% patients have VTE recurrence in 10 years after an unprovoked VTE, and 25-50% patients will develop post-thrombotic syndrome (PTS), causing long-term morbidity. Therefore, there is significant room for improvement. To accomplish this, it is crucial to have a better understanding of the pathophysiology of VTE and its complications. Although some important biomarkers in VTE were identified, the detailed hemostatic, inflammatory, and lipidomic biomarker profiles in patients after an acute VTE and their evolution and interplay in relation to treatments are unclear. A better understanding can help to identify promising targets to develop novel therapy.

The first aim of the study is to investigate important biomarkers in acute VTE as below:

### 1) *Hemostatic profile:*

In acute VTE, patients' pro-coagulation, anti-coagulation, and fibrinolytic systems are highly activated. The routine clinical coagulation assays such as prothrombin time and activated partial thromboplastin time terminate at initial clot formation, and are inadequate for comprehensive assessment of the coagulation system. In contrast, thrombin generation assays are increasingly used to assess the global hemostatic status. High thrombin generation potential or high thrombin peak concentration was correlated with increased risk of first and recurrent VTE. However, the thrombin generation profiles in acute VTE and their changes with anticoagulation have not been solidified. Therefore, thrombin generation will be used as our primary biomarker of interest. Secondly, a product of fibrinolysis, D-dimer, indicates ongoing fibrin formation and degradation. Elevated D-dimer after the completion of anticoagulation has been shown to predict increased risk of recurrent VTE. Therefore, we will also follow D-dimer during and after acute VTE. Thirdly, tissue factor (TF) and

tissue factor pathway inhibitor (TFPI) play essential roles in the initiation and modulating of blood coagulation cascade and are of interest in the process of venous thrombosis. We therefore plan to study these biomarkers in our patient population as well.

2) *Inflammatory profiles:*

Inflammation and coagulation are closely intertwined. Inflammatory diseases are associated with increased risk of VTE, and thrombosis is associated with release of inflammatory cytokines. However, their changes in relate to anticoagulation and statins are unclear, and therefore selected inflammatory biomarkers including IL-6, IL-8, tumor necrosis factor (TNF)- $\alpha$ , high sensitivity C-reactive protein (hs-CRP) will be evaluated.

3) *Lipidomic profiles:*

Serum phospholipids play crucial roles in inflammation and serve as the substrate for phospholipase A2 (PLA2), which subsequently liberates arachidonic acid for cyclooxygenase (COX) and lipoxygenase (LOX) to generate eicosanoids. In addition, these bioactive phospholipids play a major role in inflammation and repair. However, the quantification of these bioactive lipids and the process of their modulation of inflammation during acute VTE are unclear, and this study intends to clarify it. Lipid biomarkers of inflammation that will be analyzed in the study include free fatty acids and eicosanoids.

Statins are effective in the prevention of arterial thrombosis. Recently, arterial and venous thrombosis are shown to share common pathophysiological mechanisms, and effective therapies for arterial thrombosis could provide benefits in VTE. Several observational studies and the JUPITER trial, a large, randomized, placebo-controlled study, demonstrates that statins significantly reduce the risk of first VTE by 40-50%. Additionally, as few as 3 days of atorvastatin increase plasma fibrin clot permeability and susceptibility to lysis. These promising results, as well as their safety profiles, make statins an attractive potential addition to the standard anticoagulation for treating acute VTE, in an effort to reduce long-term morbidity.

Our second aim is to determine the actions of statins on the proposed biomarkers in acute VTE because: First, the effects of statins on thrombin generation in patients with acute VTE have not been studied. A study in patients with atrial fibrillation on warfarin showed a 40% reduction in endogenous thrombin potential with only three months of intensive cholesterol-lowering treatment including statins. Similar effects could be seen in patients with acute VTE. In addition, previous studies evaluating the effects of statins on the reduction of D-dimer or inflammatory cytokines revealed promising results but were not focused on patients with acute VTE. Therefore, this study will generate important information for acute VTE patients.

### **3.0 Patient Selection**

#### **3.1 Inclusion of Women and Minorities**

Entry to this study is open to both men and women ages 18 and older, of all racial and ethnic subgroups. This study will be conducted in accordance with the International Conference on Harmonisation and Helsinki Guidelines.

### **3.2 Inclusion Criteria**

- 3.2.1 At least 18 years old
- 3.2.2 A diagnosis of proximal DVT (proximal to and including popliteal vein), with or without PE, confirmed by objective imaging studies, such as Doppler ultrasound, venograms (for DVT) and/or computer tomography, angiograms, ventilation-perfusion scan (for PE)
- 3.2.3 Treated with warfarin or rivaroxaban as anticoagulation (short-term bridging with heparin or lovenox, if needed is allowed)

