### **3.3 Exclusion Criteria**

- 3.3.1 Thrombolysis within 6 weeks prior to enrollment
- 3.3.2 Patients with statin use within 6 weeks of enrollment
- 3.3.3 Patients with known allergy or intolerance to statins or statins are contraindicated for any other reasons
- 3.3.4 Patients with baseline aspartate aminotransferase (AST), alanine aminotransferase (ALT), or total bilirubin  $\geq 2.0 \times$  ULN (upper limit of normal)
- 3.3.5 Pregnant or breastfeeding females are excluded
- 3.3.6 Any malignancy diagnosed within the preceding 2 years, except for squamous cell carcinoma or basal cell carcinoma of skin treated with local resection only, or carcinoma *in situ* of the cervix
- 3.3.7 Incarcerated patients are excluded from the study due to the inherent difficulties in maintaining close follow-up for study purposes in patients who are incarcerated.

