### **4.0 Randomization of Patients**

Patients will be randomized at the time of registration/enrollment on this clinical trial via contact with the study nurse/coordinator at the time of the initial registration of the subject. The study nurse/coordinator will conduct the randomization on the REDCap Data Capture system and relay this information to the treating/enrolling physician so that the appropriate medication (atorvastatin) can be started.

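### Both aims concern acute VTE, but Sections 3.2.2 and 3.2.3 set no limit on time since DVT diagnosis and the analysis names no covariate for it

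*Combined protocol and SAP*

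**What the plan says.** Section 2.0 states the population of interest for each aim. For the first: "The first aim of the study is to investigate important biomarkers in acute VTE as below". For the second: "Our second aim is to determine the actions of statins on the proposed biomarkers in acute VTE". It adds that "this study will generate important information for acute VTE patients".

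The eligibility text is wider. Section 3.2.2 requires "A diagnosis of proximal DVT (proximal to and including popliteal vein), with or without PE, confirmed by objective imaging studies". Section 3.2.3 requires "Treated with warfarin or rivaroxaban as anticoagulation (short-term bridging with heparin or lovenox, if needed is allowed". Neither uses the word acute, and neither limits the time since diagnosis or the time already spent on anticoagulation. The look-backs in Section 3.3 concern thrombolysis and statin use (6 weeks each) and malignancy (2 years). None of them limits the age of the clot.

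Under Section 4.0 randomization takes place at enrolment: "The study nurse/coordinator will conduct the randomization on the REDCap Data Capture system". No stratification factor is stated. The primary objective (Section 1.1.1) is "To determine the reduction of thrombin peak concentration and/or endogenous thrombin potential measured by Thrombin Generation Assay (TGA) at 3 months", compared between arms. Sections 6.0, 9.2.1 and 10.0 count visits from enrolment.

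Section 20.0 sizes the trial on a two-sample t test. It also plans linear mixed models with an arm-by-time term and a general commitment to adjust for potential confounders, none of which is named.

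**The concern.** A patient months after diagnosis and stable on warfarin or rivaroxaban meets Section 3.2 and is not excluded by Section 3.3. Such a patient lies outside the question that Section 2.0 poses.

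This bears on the endpoint because the plan speaks of a reduction. Section 2.0 (hemostatic profile) describes the coagulation and fibrinolytic systems as highly activated in acute VTE, and says that the course of thrombin generation under anticoagulation is not yet established. On that reasoning, a baseline taken days after the clot and one taken on long-established anticoagulation need not measure the same thing, and neither need the change to month 3. The month-3 Doppler for residual vein obstruction and the post-thrombotic assessments would also fall at different clot ages in different patients.

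At stake are how well the result answers the acute-VTE question, and possibly the precision of the primary comparison.

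**Working it through.** **1. Is there a limit anywhere in the operative text?**

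| Place | Recency limit | Limits time since DVT? |
|---|---|---|
| 3.2.2 index event | none | no |
| 3.2.3 anticoagulant | none; bridging allowed if needed | no |
| 3.3.1 thrombolysis | 6 weeks | no |
| 3.3.2 statin use | 6 weeks | no |
| 3.3.6 malignancy | 2 years | no |
| 4.0 randomization | no stratification factor stated | no |
| 20.0 analysis | covariates not named | no |

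**2. The plan's own power figure.** Inputs from Section 20.0: 33 evaluable per arm, effect 0.7 SD, two-sided alpha 0.05, two-sample t test. The exact noncentral-t calculation gives 80.0% power at 33 per arm (33.02 per arm are needed for 80%). The normal approximation gives 81.2%. The stated figure reproduces. The target of 80 allows for 1 - 66/80 = 17.5% non-evaluable.

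**3. What a mixed population could cost.** The documents give neither the share of late patients nor how their change differs, so both are assumptions. Let a share f be late, with mean change shifted by m planning SDs, equally in both arms. The extra variance, as a fraction of the planning variance, is

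v = f(1 - f)m²,

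and the standardized effect becomes 0.7/√(1 + v).

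| f | m | v | SD ratio | Effect | Power at 33 per arm | Per arm for 80% |
|---|---|---|---|---|---|---|
| 0 | - | 0 | 1.000 | 0.700 | 80.0% | 34 |
| 0.2 | 0.5 | 0.040 | 1.020 | 0.686 | 78.4% | 35 |
| 0.3 | 0.5 | 0.0525 | 1.026 | 0.682 | 77.9% | 35 |
| 0.2 | 1.0 | 0.160 | 1.077 | 0.650 | 73.9% | 39 |
| 0.3 | 1.0 | 0.210 | 1.100 | 0.636 | 72.1% | 40 |

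The last column is the exact t requirement rounded up, so the planned case shows 34 (33.02 rounded up). In the last row, 80% power needs all 40 enrolled per arm to be evaluable, which uses up the drop-out allowance.

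**4. What adjustment does.** In this illustration v is variance between early and late patients. A covariate that captures that difference removes it and returns the residual variance to the planning value. The unadjusted t test leaves it in.

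**The case against.** **The surrounding text points to recent cases.** Bridging is allowed at entry, a month-3 Doppler is described as standard care for everyone, and the month-9 comparison of patients on and off anticoagulation fits a finite course begun near enrolment. This is fair. A reader might infer from Section 3.2 that the sponsor means to enrol patients years after the event; the documents do not support that. But these are hints, not limits, and eligibility is decided by Section 3.2.

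**The schema is not shown in the text available for review and may state a window.** This stands. The finding is that Section 3.2 has no window, not that none exists anywhere.

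**The thrombolysis exclusion.** A reader might take "Thrombolysis within 6 weeks prior to enrollment" as proof that enrolment weeks after the clot was foreseen. It is not. A look-back of this kind works equally well with enrolment at diagnosis, and prior statin use has the same 6 weeks.

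**Confounders are already to be adjusted for.** Section 20.0 does say so, and medical history is taken at every visit. Time since diagnosis could therefore be added later, but it is not pre-specified, and the sentence does not reach the t test that sized the trial.

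**Nothing shows that late patients raise the SD.** This also stands. The 0.7 SD rests on cited studies in atrial fibrillation and in diabetes, not on an acute VTE sample. Patients on settled anticoagulation might even vary less than patients sampled at different points in the first days. The effect is also smaller if month-3 values alone are compared.

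**Conclusion.** The mismatch between the acute-VTE aims and the eligibility text holds, and it is worth correcting before analysis. No stated number is wrong.

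The consequence is moderate. Randomization keeps the arm comparison unbiased in expectation, so bias in the treatment effect should not be inferred. What remains is a looser fit to the acute-VTE question, possible chance imbalance with about 33 per arm, and possibly lost precision. The fall in power from 80% to about 72-78% is conditional on 20-30% late patients, a shift of 0.5-1 SD and the same shift in both arms. None of these comes from the documents.

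Two stronger readings are tempting. The first is a fall in power to 65% or 58%. Those figures follow from SD inflation of 20% or 30%, which is 44% or 69% extra variance. With 30% late patients, that requires mean shifts of √(0.44/0.21) = 1.45 SD or √(0.69/0.21) = 1.81 SD, and nothing in the documents points to shifts of that size. The second is that the result could not be applied to acute VTE. That would be so only if many late patients enrolled, which is unknown.

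**What to change.** 1. Reconcile Section 3.2.2 with the aims by stating a maximum interval from objective diagnosis to randomization. The length is for the sponsor to choose, consistent with the schema if it gives one. The cost is one line, and some late referrals become ineligible. The planned sample size does not change.

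2. Record the date of diagnosis as a data item; the medical history in Section 6.0 can supply it. In Section 20.0, name days from diagnosis to randomization and the baseline value as covariates in the month-3 model for thrombin peak and for endogenous thrombin potential, with their functional form fixed in advance. This costs one field and one sentence. It is worth doing even if few late patients are expected, and it still helps for any patients enrolled before a window is added.

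3. Report the distribution of time since diagnosis by arm, so that readers can judge how far the sample represents acute VTE.

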## 6.0 Study calendar

	Initial visit	3 month 	9 month 
Singed informed consent	x		
Medical/treatment history	x	x	x
Physical examination	x	x	x
Vital signs	x	x	x
CBC with diff	x	x	x
Chemistry, including liver function tests	x	x	x
Fasting lipid profiles	x	x	x
hs-CRP	x	x	x
D-dimer	x	x	x
Urine <math>\beta</math>-hCG	x		
Thrombin generation assay	x	x	x
IL-6, IL-8, TNF-<math>\alpha</math>	x	x	x
Lipidomic profiles	x	x	x
Doppler ultrasound of bilateral lower extremities		x	
Prescription of statins	x	x	

All scheduled visits are allowed a window of +/- 21 days

CBC includes: white blood cells with differential, hemoglobin, red blood cells, and platelets

Chemistry and liver function tests include: sodium, potassium, carbon dioxide, glucose, BUN, creatinine, calcium, total protein, albumin, bilirubin, alkaline phosphatase, AST and ALT

Required only in women of child-bearing potential

Lipidomic profiles includes free fatty acids, lipoprotein-associated phospholipase A2, pro-inflammatory eicosanoids

Prescription of statins only in the statin arm

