## **16.0 Thrombin generation assay**

Blood samples for measurement of thrombin generation will be drawn in vacutainer tubes containing 3.2% sodium citrate with and without corn trypsin inhibitor (CTI) and be processed appropriately within an hour prior to storage. Blood samples will be centrifuged at 2500g (relative centrifugal force) for 15 minutes (min). Plasma will be transferred into plastic tubes, and re-centrifuged at 2500g for 15 min. Plasma will be decanted again after second spin and stored in aliquots of 0.2 mL (platelet poor plasma). The platelet poor plasma will then be snap frozen and stored at -70°C until testing as bulk at the end of the study.

The thrombin generation assays will be performed using a commercial kit (TECHNOTHROMBIN® TGA, Technoclone, Vienna, Austria) according to the manufacturer's instructions in [name] laboratory. The assays are performed based on monitoring the fluorescence generated by thrombin cleavage of a fluorogenic substrate over time, after the activation of the coagulation cascade by tissue factor. At least two reagents will be used. Parameters that will be recorded include: lag phase, time to peak thrombin concentration, peak thrombin concentration, and endogenous thrombin potential (measured by area under the curve).

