**20.0 Statistical Analysis**

At least 66 evaluable patients will be randomized (1:1 allocation, 33 evaluable patients in each arm) into "anticoagulation" versus "anticoagulation +atorvastatin" arms. The primary endpoints are thrombin peak and thrombin generation. Based on the published data, we anticipate an 80% power to detect an effect size of 0.7 standard deviations in the reduction of thrombin peak or thrombin generation between the two arms with two-side alpha of 0.05 using a two-sample t test. An overall alpha of 0.1 for this pilot study was split into 0.05 for each endpoint (thrombin peak and thrombin generation) using Bonferroni method. Considering possible drop-outs, our target enrollment will be 80 patients, with 40 on each arm.

All data will be collected on study-approved data collection forms and entered into Research Electronic Data Capture (REDCap), which is a secure, web-based application designed to support data capture for research studies by building and managing online surveys and databases. The system was built with the help of the OSU Research Informatics Services.

Descriptive statistics (i.e. means, standard deviations, 95% confidence intervals for continuous variables, and frequencies for discrete data) and graphical analyses will be used for all clinical outcomes, demographics, VTE related events, laboratory results, and adverse events for each arm. The secondary endpoints will be compared between the two arms using chi-square test or Fisher's exact test, whichever is appropriate. The associations between treatment type and the change in biomarkers will be evaluated using two-sample t test. Log-transform will be used if necessary. Linear mixed models will be used to study the associations between the primary endpoints and treatment, and trend across time. The interaction term "arm x time" will be included in the model to study whether the two treatment arms have different "behavior" across time. Potential confounders will be included in the models. Thrombin peak concentration and

endogenous thrombin potential at 9 months will be compared between the patients on anticoagulation and those off anticoagulation.

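### Optional precision gain: Section 20.0 could make the 3-month primary comparison a baseline-adjusted model instead of an unadjusted t test

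*Combined protocol and SAP*

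**What the plan says.** Section 1.1 sets the primary objective as the "reduction of thrombin peak concentration and/or endogenous thrombin potential measured by Thrombin Generation Assay (TGA) at 3 months", comparing the two arms. Section 20.0 powers this for 33 evaluable patients per arm and an effect of 0.7 SD in the "reduction of thrombin peak or thrombin generation between the two arms with two-side alpha of 0.05 using a two-sample t test". No covariate enters that test. Section 4.0 names no stratification factor.

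Section 20.0 goes further: "Linear mixed models will be used to study the associations between the primary endpoints and treatment, and trend across time". It adds: "Potential confounders will be included in the models". The confounders are not listed, and neither the t test nor the mixed model is named as primary.

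Two variables are collected at entry by design. The Section 6.0 calendar schedules the "Thrombin generation assay" at the initial visit as well as at 3 and 9 months. The entry criterion in Section 3.2 fixes the oral anticoagulant as one of two drugs: "Treated with warfarin or rivaroxaban as anticoagulation (short-term bridging with heparin or lovenox, if needed is allowed". Section 16.0 says that thrombin generation samples are stored "until testing as bulk at the end of the study".

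**The concern.** With 66 evaluable patients and 80% power there is no slack. Variation that could be predicted from a patient's own baseline stays in the residual variance of an unadjusted test. So does any difference between patients on the two drugs. If the reduction means change from baseline, baseline is used by subtraction only, which is not the same as adjusting for it.

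Adjustment is clearly contemplated, but neither the covariates nor the primary model is fixed. The stake is precision. Randomisation protects the comparison from systematic bias, and the unadjusted test holds its nominal error rate.

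**Working it through.** **Inputs from Section 20.0.** 33 per arm, effect d = 0.7 SD, two-sided alpha 0.05 per endpoint, two-sample t test.

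**Inputs assumed.** The SD is equal at both visits. The correlation r between baseline and 3 months, the drug mix p and the between-drug difference D are not in the documents, so ranges are shown.

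**1. The plan's own figure.** Noncentrality = 0.7 × √(33/2) = 2.843 on 64 df, which gives power 79.97%. The sizing reproduces.

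**2. Baseline covariate, 0.7 in SDs of the 3-month value.** The residual SD shrinks by √(1 − r²), so the effective d = 0.7/√(1 − r²), on 63 df.

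| r | effective d | power |
|---|---|---|
| 0.1 | 0.704 | 80.3% |
| 0.2 | 0.714 | 81.5% |
| 0.3 | 0.734 | 83.5% |
| 0.5 | 0.808 | 89.8% |

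The formula counts the lost degree of freedom but not chance imbalance in baseline, so at low r it is slightly optimistic (see step 5).

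**3. Baseline covariate, 0.7 in SDs of change.** The SD of change is √(2(1 − r)) times the SD of a single value. The raw effect is therefore 0.7 × √(2(1 − r)), and after adjustment the effective d = 0.7/√((1 + r)/2).

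| r | raw effect, 3-month SDs | t test on change | plain 3-month t test | baseline-adjusted, formula | baseline-adjusted, simulated |
|---|---|---|---|---|---|
| 0.3 | 0.828 | 80.0% | 91.2% | 93.5% | 93.1% |
| 0.5 | 0.700 | 80.0% | 80.0% | 89.8% | 89.3% |
| 0.7 | 0.542 | 80.0% | 58.3% | 85.9% | 85.3% |

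Fixing 0.7 in change units makes the raw effect larger when r is low, so the first row flatters the covariate. At r = 0.3, about 11 points of the gain (80.0% to 91.2%) come from not subtracting baseline, and about 2 (91.2% to 93.5%) come from the covariate. At r = 0.5 the whole gain comes from the covariate.

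**4. Drug covariate.** With a share p on one drug and a difference D (in within-drug SDs of the analysed endpoint), the SD in the unadjusted test grows by √(1 + p(1 − p)D²). If 0.7 is a within-drug SD, unadjusted power is:

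| D | 50:50 mix | 80:20 mix |
|---|---|---|
| 0.25 | 79.4% | 79.6% |
| 0.5 | 77.5% | 78.4% |
| 1 | 70.7% | 73.9% |

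If 0.7 is already the SD of the mixed population, nothing is lost against plan. Adjusting for drug would then raise power to 82.3% or 87.9% (50:50) and 81.5% or 85.4% (80:20), at D = 0.5 or 1. A gap that is the same at both visits cancels in a change score (simulated power 79.8% at a gap of 1 SD).

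Simulated effect of adding drug once baseline is in the model (effect 0.7 SD of change, r = 0.5):
- no drug difference: 89.3% to 88.9%
- D = 0.5: 86.9% to 89.0% (50:50), 87.8% to 88.9% (80:20)
- D = 1: 79.2% to 88.9% (50:50), 83.1% to 88.9% (80:20)

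**5. Downside and error rate.** This was simulated at r = 0 with no drug difference and an effect of 0.7 SD of the 3-month value. Baseline alone gives 79.2%, and both terms give 78.5% to 78.6%. Against 79.97%, that is a loss of about 0.7 and 1.4 points. Taking 0.7 off the 80.3% at r = 0.1 leaves no gain there. Simulated type I error was 4.6% to 5.3% for every model.

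**The case against.** The strongest reply is that nothing here is wrong. The t test is valid and correctly sized, and the study is an open-label pilot. Section 20.0 already plans mixed models for the primary endpoints with covariates, and a change score already uses baseline. All of this stands, and it is why the point is optional. What remains is that subtraction is not adjustment, that the covariates are unnamed, and that no analysis is designated primary.

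A second reply also stands in part: r may be low. The enrolment sample is taken in acute disease and possibly during bridging. At r = 0.1 to 0.2, in 3-month units, the gain is nil to about 1.5 points.

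Three stronger readings are tempting, and the documents do not support them.
- *The mix of two anticoagulants leaves the trial underpowered or biased.* No document figure shows that the drugs differ on these endpoints or gives the mix, and randomisation excludes systematic bias.
- *The 0.7 SD is invalid because it comes from warfarin patients.* Section 2.0 does describe one of the two sources cited for the sizing that way ("A study in patients with atrial fibrillation on warfarin showed a 40% reduction in endogenous thrombin potential"). But Section 20.0 does not show how 0.7 was derived, so no mismatch can be demonstrated.
- *The plan ignores covariates.* The mixed-model sentences show otherwise.

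**Conclusion.** This is an optional improvement to Section 20.0, not an error. Prespecifying baseline as a covariate in the 3-month comparison is worth roughly 0 to 10 points of power for r from 0.1 to 0.5 if the effect is in 3-month SDs. It is worth roughly 5 to 13 points over a t test on change for r from 0.7 down to 0.3 if the effect is in change SDs, with the caveat that most of the gain at r = 0.3 comes from dropping the subtraction. The adjusted model does well across the range, whereas the change score and the plain 3-month value each lose ground at one end of it.

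The case for the drug term is weaker. At a 50:50 mix it adds about 2 points if the drugs differ by 0.5 SD and 9 to 10 if they differ by 1 SD; it adds less at 80:20, and it costs about half a point if they do not differ. All of these sizes rest on assumed r, D and mix, so the actual gain cannot be known from the documents.

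**What to change.** In Section 20.0, state that the primary 3-month analysis of each endpoint is a linear model with arm and the baseline value of the same assay. Put baseline on the same scale as the outcome, so that both are log-transformed if either is. The oral anticoagulant recorded at randomisation may be added as a second prespecified covariate. Say how a missing baseline sample is handled. Name the mixed models as supportive and list their covariates, entering baseline either as a covariate or as the first repeated measure, not both.

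The cost is a few sentences, with no new data and no change to randomisation or sample size. Section 15.0 suggests that enrolment is under way, but because the assays are run in bulk at the end, the change can still precede any primary-endpoint result if it is made before that testing starts. The worst-case price is the loss shown in step 5.
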